Isosorbide Mononitrate For Anti-Vascular Endothelial Growth Factor (VEGF) Induced Kidney Injury

NCT04051957

Version Date: 10/24/2019

1 Isosorbide Mononitrate For Anti-Vascular Endothelial Growth Factor (VEGF) Induced Kidney
2 Injury

3
4 **SPECIFIC AIM:**

5 To test the hypothesis that isosorbide mononitrate prevents deterioration of renal function in patients
6 receiving anti-angiogenic therapies that target vascular endothelial growth factor (VEGF).
7
8
9
10
11
12
13
14
15
16
17
18
19
20
21
22
23
24
25
26
27
28
29
30
31
32
33
34
35
36
37
38
39
40
41
42
43
44
45
46
47
48
49

BACKGROUND AND SIGNIFICANCE: Anti-angiogenic drugs that target VEGF (bevacizumab) and its receptors (sunitinib, sorafenib, pazopanib, and axitinib) are part of standard treatment for patients with renal cell carcinoma, non-small cell lung carcinoma, colorectal carcinoma, and gastrointestinal stromal tumors¹. However, because of their action on VEGF expression levels, the use of these medications has been associated with significant kidney damage and hypertension. Indeed, the use of anti-angiogenic therapies is frequently halted in cancer patients because of worsening kidney function, hypertension, and proteinuria with the subsequent delay, interruption or reduction of effective dose in patients requiring this treatment modality¹.

Importantly, many of the kidney-related side effects of antiangiogenic and anti-VEGF therapies have been attributed to the downregulation of nitric oxide (NO) bioavailability¹. In support of a modulatory effect of VEGF on NO, it has been shown that VEGF infusion results in a significant drop in blood pressure mainly through stimulation of eNOS (endothelial NO synthase) and consequent NO release^{2,3}. NO activation and enhanced synthesis lead to vasodilation in the renal microvasculature, which results in lowering of blood pressure and other modulatory effects on kidney function.

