SAFETY OF ISOSORBIDE MONONITRATE: The FDA indication for IMN is for prevention of angina pectoris (<https://druginserts.com/lib/rx/meds/imdur/>). Per the package insert as referenced in link, there is no evidence of carcinogenicity, gene mutation or chromosome aberrations at biologically relevant concentrations. Side effects include nausea, dizziness, headache, symptomatic hypotension

1
2
3
4
5
6
7
8
9
10
11
12
13
14
15
16
17
18
19
20
21
22
23
24
25
26
27
28
29
30
31
32
33
34
35
36
37
38
39
40
41
42
43
44
45
46

MATERIAL AND METHODS:

Study Population: Adult patients who are referred to the Adult Nephrology Clinic at The University of Texas Health Science Center at Houston for evaluation and treatment of acute kidney injury, hypertension and/or proteinuria while either on or enrolled with anti-VEGF therapies, will be included in the study. The protocol is currently being submitted to the University of Texas Health Science Center at Houston IRB. Informed consent in the native language of each patient will be obtained prior to enrollment.

Inclusion Criteria: Patients on or enrolled for anti-VEGF therapy and having new-onset proteinuria, defined as a urine protein: creatinine ratio (UPC) of >500mg/g or hypertension (Systolic BP \geq 140 mm Hg and/or diastolic BP \geq 90 mm Hg) or a decrease in eGFR by \geq 25% from baseline before starting therapy.

Exclusion Criteria: Pregnant women and breast-feeding women. Patients >65 years will be excluded.

Protocol and Treatment Plan: The patients will have baseline blood pressure (BP), UPC, weight, serum basic metabolic panel and eGFR measured prior to being assigned into groups. All current prescribed and over the counter medications will be documented. Patients will be allocated to the treatment or placebo arms by simple randomization. BP will be measured in the right arm of patients, in the seated position, using arm cuff and automated office blood pressure by oscillometry method. Three measurements will be taken one minute apart, and the average of each of the systolic and diastolic measurements will be charted as the blood pressure recording for the visit. Pregnancy and breast feeding status will be established by self-reporting by female patients.

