7 appointments would be +/- 3 days to account for clinic closure, weather changes or patient's inability to
8 come to clinic due to non-medical reasons. A follow up phone call will be done every month (weeks 6,
9 10, 14 and 17 weeks) for 3 months. Antihypertensive medications that the patients have been taking
10 prior to enrollment will be continued. Any reduction in the need for antihypertensive medications will
11 be documented. UPC will be measured at the time of enrollment and then monthly.

12
13 **Primary End Points:**

- 14
- Reduction in UPC of $\geq 25\%$ from that measured before enrollment

15 **Secondary End Points:**

- 16
- Improved eGFR $\geq 25\%$ from before enrollment.
 - Reduction in SBP of ≥ 10 mm Hg and/or DBP ≥ 5 mm Hg from before enrollment
- 17
18

19 Both the primary and secondary outcomes will be measured for every month for the 3 months that the
20 patient is in the trial. All patients will continue treatment for the entire 3 months to help with data analysis
21 for future larger randomized controlled studies. The grace period for follow up appointments would be
22 +/- 3days to account for clinic closure, weather changes or patient's inability to come to clinic due to
23 non-medical reasons.

24 **MONITORING/ EVALUATION DURING STUDY:**

25 Baseline BP, serum creatinine, eGFR, and UPC will be recorded at the time of enrollment. For blood
26 testing 2cc of serum will be collected and for urine testing 2 ml of urine will be
27 collected, and sent to the Memorial Herman outpatient laboratory. Blood pressure will
28 be monitored on a weekly basis starting from the time of enrollment. In those who are already on BP
29 medications, BPs will be recorded on a weekly basis, and any need for reduction/increase in the
30 doses/addition of new medications will be document. Patients will be given a log book
31 to record their BPs. Patients will be monitored for 3 months. UPC and serum creatinine will
32 be measured on a monthly basis.

33 If side effects (nausea, dizziness, headache, symptomatic hypotension) are observed to the increased
34 dose of 120 mg/day, the dose will be reduced back to the 60 mg d.

35 **Confidentiality Plan:**

36 All data obtained, including concomitant medications will be entered in Red Cap. All serious adverse
37 events will be forwarded to FDA according to the UT Health Science Center at Houston institutional
38 policy. All records will be maintained at UT Heath Science center. The Data Safety Monitoring board

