39 will be involved in safety monitoring.

40 **Possible Side Effects:**

41 Minor side effects of Imdur have been noted, including headache, dizziness, hypotension and nausea.
42 As per FDA approved package insert, headache and dizziness was reported in $>5\%$ of the patients. These
43 symptoms are dose dependent and tend to disappear with continued use.

1 Criteria for Removal:

2 With the increased dose of Imdur, if side effects such as symptomatic hypotension, nausea, headache
3 or dizziness the dose will be reduced to 60 mg ER. If it is the starting dose (60 mg ER) which caused
4 these effects, then the patient will be taken off the drug, and will be observed for Intension to Treat
5 (ITT) analysis. The Severe Adverse Effect (SAE) will be reported according to the UT Health Science
6 Center at Houston institutional policy. Criteria for removal would be uncontrolled nausea, headache,
7 symptomatic hypotension or dizziness. We will also monitor for any worsening of renal function or
8 proteinuria.

9 Limitations:

10 This is a pilot study and therefore it is may not be powered to detect difference with treatment. The small
11 sample size may not allow the data to be statistically significant. It is unclear if other antihypertensive
12 medications will confound the results. Once preliminary data is available, the study population will be
13 increased for a larger clinical trial.

14

15 Expected results:

16 There will be statistically significant response seen with therapy in the patients. The study is a pilot study
17 and will help in establishing the basis of a larger randomized controlled study.

REFERENCES:

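### The aim is to prevent loss of renal function, but no primary or secondary endpoint records an eGFR decline, and a patient with one can still be a primary success

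*Protocol*

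**What the plan says.** The Specific Aim reads: "To test the hypothesis that isosorbide mononitrate prevents deterioration of renal function in patients" on anti-VEGF treatment. Background and Significance says that such treatment is often halted "because of worsening kidney function, hypertension, and proteinuria", so kidney function and proteinuria are named as separate harms.

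Inclusion Criteria accept any one of three routes: proteinuria, hypertension, or "a decrease in eGFR by \geq 25% from baseline before starting therapy".

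Primary End Points has one item, a fall in UPC of at least 25% "from that measured before enrollment". Secondary End Points has a blood pressure item and one eGFR item: "Improved eGFR $\geq 25\%$ from before enrollment". Both sets of outcomes are assessed monthly for three months.

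Criteria for Removal adds "We will also monitor for any worsening of renal function or" proteinuria. It gives no threshold for worsening and no link to how an endpoint is scored. Study design sets 20 patients per group under double blinding.

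**The concern.** The aim is about preventing a decline, while the endpoints count only improvements. The primary endpoint looks at proteinuria alone. The eGFR endpoint is cut at a 25% gain, so everything from a 24% gain to a severe loss falls in one category. If the drug slowed the loss of eGFR, no endpoint would show it; if it hastened the loss, no endpoint would show that either.

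Interpretation is what is at stake. A higher UPC response rate on active treatment could be reported as support for the aim although some responders had lost filtration. The protocol says that this pilot is to form the basis of a larger randomized trial, so the gap could be carried forward.

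**Working it through.** **Inputs from the protocol:** the two endpoint definitions, the 25% eGFR entry criterion, monthly UPC and creatinine/eGFR, and 20 patients per group. The protocol gives no figure for how often UPC and eGFR fall together, so there is no figure of its own to reproduce.

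**Step 1. Apply the rules to illustrative patients.** All three have UPC 1000 to 740 mg/g: (1000 − 740)/1000 = 26% fall.

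| Patient | eGFR | Change | Primary (UPC) | Secondary (eGFR gain ≥25%) |
|---|---|---|---|---|
| A | 60 to 60 | 0% | met | not met |
| B | 60 to 42 | (42 − 60)/60 = −30% | met | not met |
| C | 60 to 75 | (75 − 60)/60 = +25% | met | met |

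A and B have identical endpoint records. B's loss is larger than the 25% that the protocol accepts for entry.

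**Step 2. Check the reference point of the 25%.** At entry the fall is counted from before therapy. A fall counted from enrollment is a different quantity. For a patient who entered with exactly a 25% loss, a further 25% leaves 0.75 × 0.75 = 0.5625 of the pre-therapy value, a total loss of about 44%. The size can be borrowed from the entry rule, but not the reference point.

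**Step 3. Weight of one patient.** 1/20 = 5 percentage points of an arm's response rate. That holds for any patient, and is not the excess caused by an eGFR fall.

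**Step 4. How much could an eGFR fall itself raise the chance of UPC success?** This needs two assumptions that the protocol does not supply: a single-sample log-UPC SD *s* of 0.25 to 0.45, and the coupling between UPC and filtration. With full one-for-one coupling and an eGFR fall *g*,

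P(success) = Φ[(ln 0.75 − ln(1 − *g*)) / (*s*√2)].

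| eGFR fall | *s* = 0.25 | *s* = 0.35 | *s* = 0.45 |
|---|---|---|---|
| 0% | 0.21 | 0.28 | 0.33 |
| 25% | 0.50 | 0.50 | 0.50 |
| 40% | 0.74 | 0.67 | 0.64 |

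The 0.50 is an identity (ln 0.75 − ln 0.75 = 0) and carries no information about *s*. The excess over a stable patient, times 5 points, is:
- 25% fall: 5 × (0.500 − 0.326) = 0.9 to 5 × (0.500 − 0.208) = 1.5 points per patient.
- 40% fall: 5 × (0.637 − 0.326) = 1.6 to 5 × (0.736 − 0.208) = 2.6 points per patient.

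With no coupling the term ln(1 − *g*) drops out, every row equals the first, and the excess is zero. The range is therefore 0 to about 2.6 points per such patient.

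**Step 5. What would an eGFR condition on the primary endpoint do?** Assume UPC response of 50% vs 25%, 20 per arm, two-sided 5% test of two proportions. A share of UPC responders in each arm is reclassified for an eGFR fall.

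| Share reclassified (active, control) | Conditioned rates | Difference | Power |
|---|---|---|---|
| 0%, 0% | 50.0% vs 25.0% | 25 points | 37% |
| 10%, 10% | 45.0% vs 22.5% | 22.5 points | 32% |
| 30%, 10% | 35.0% vs 22.5% | 12.5 points | 14% |

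The rates and shares are assumptions and show a range only.

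**The case against.** The strongest reply is that any endpoint in one domain can be met while another domain worsens, and that this is a choice rather than a mistake. That would settle the matter if the aim concerned proteinuria. It does not, because the stated aim is deterioration of renal function and the eGFR endpoint cannot show it either.

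A second reply is that eGFR is measured monthly, worsening is monitored and a safety board is involved. A decline would indeed be seen. It would still have no definition and no comparison between arms among the endpoints. A cross-table alone could be left to a statistical analysis plan, but the endpoint list is fixed in the protocol.

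Two stronger readings are tempting, and the protocol supports neither.
- A reader might infer that the deterioration is itself counted as success. What is counted is the UPC fall; the eGFR loss is simply ignored.
- A reader might infer that the scoring favours the active arm, because the drug lowers blood pressure and symptomatic hypotension is a listed side effect. The protocol does not say that the drug reduces filtration or that lower filtration reduces UPC, and its Background argues for vasodilation in the renal microvasculature. UPC is a ratio to urine creatinine, so one-for-one coupling also needs creatinine excretion to stay unchanged. Loss of eGFR from the anti-VEGF drug or from background antihypertensives can occur in both arms. No imbalance is shown.

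The objection to building an eGFR condition into the primary endpoint also stands in part. It would make the primary result depend on a single monthly creatinine, and power could fall even with equal reclassification (37% to 32% in the illustration).

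**Conclusion.** The point holds as a mismatch between aim and endpoints. A patient who loses 25% or more of eGFR after enrollment can be a primary success, and no primary or secondary endpoint records the loss. This follows from the definitions alone and needs no numerical assumption.

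The size of any effect on the treatment comparison is unknown. On assumed SDs, and with coupling anywhere from none to one-for-one, the excess is 0 to about 2.6 percentage points of an arm's response rate per patient with a 25% to 40% eGFR fall. It biases the comparison only if such patients are more frequent in one arm. The evidence does not require replacing the primary endpoint. It does call for the decline to be scored, and for UPC response not to be reported as evidence on renal function by itself.

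**What to change.** Keep the UPC primary endpoint. In the endpoint section of the protocol:

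1. Add a secondary endpoint: eGFR at least 25% below its enrollment value, scored at each monthly visit and compared by arm. State that the 25% is borrowed in size from the entry rule but is measured from enrollment.
2. Add a prespecified supportive analysis of UPC response without such an eGFR fall at the same visit. Show the table of UPC response by eGFR fall for each arm.
3. State that UPC response alone will not be reported as an improvement in, or protection of, renal function.

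This takes a few sentences and no new measurement, since UPC and creatinine/eGFR are already collected monthly. It costs one more secondary comparison in a 40-patient pilot. The supportive response rate may be lower than the primary one, and noise in a single creatinine value will misclassify some patients.

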Patients in the treatment arm will be started on IMN 60 mg ER daily. The dose of IMN will be escalated to 120 mg ER (two tablets of 60 mg ER) after 4 weeks of start of therapy, if no response as per our response criteria (as below) is achieved. The grace period for follow up appointments would be +/- 3days to account for clinic closure, weather changes or patient's inability to come to clinic due to non-medical reasons.

The drug and placebo will be compounded in Compounding Shop Pharmacy, [name]. Even though we will be using the drug for a non-FDA approved use of IMN, we will not be needing IND for the study drug due to the low risk profile of the drug. Drug accountability by IDS will include for storage, labeling, dispensing and disposal of the study drug and placebo.

Criteria for Response (one or more of the following)

1. Improved eGFR \geq 25% from prior to enrollment.
2. Reduction in proteinuria of \geq 25% from prior to enrollment.
3. Reduction in SBP of \geq 10 mm Hg and/or DBP \geq 5 mm Hg from prior to enrollment

Study design:

The patients will be allocated by simple randomized into the two groups (20 patients per group). The study will be double-blinded

Group 1: (Treatment group). The starting dose will be Imdur 60 mg ER daily and after 4 weeks, if tolerated but response is not achieved, the dose will be escalated to Imdur 120 mg ER daily (2 tabs of 60 mg ER tablets). This would be done in addition to the standard of care treatment with either angiotensin converting enzyme inhibitor (ACEI) or calcium channel blockers to treat hypertension as needed.

Group 2: (Placebo group): Placebo will be given along with the standard of care treatment with either ACE I or calcium channel blockers to treat hypertension as needed. The tablets of placebo will be doubled after 4 weeks of start of therapy. This will help eliminate bias in this double-blinded study.

1
2 **Follow-up:** Systolic BP will be monitored on a weekly basis for three months. The patients will
3 record their BPs at home with their automated machines and will either call in with the results or bring
4 their records during the next clinic visit. The eGFR and serum creatinine (included in the basic
5 metabolic panel) will be measured as per protocol laboratory workup done within 15 days of
6 enrollment. This will be done once a month during clinic visits. The grace period for follow up

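### The blood pressure secondary endpoint is an either/or threshold on data charted as numbers; under plausible assumptions it loses roughly half the effective sample size against a baseline-adjusted mean comparison.

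*Protocol*

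**What the plan says.** Under Secondary End Points, the protocol defines blood pressure success as a fall in SBP of at least "10 mm Hg and/or DBP" of at least "5 mm Hg from before enrollment". This is a yes/no outcome that either pressure can satisfy.

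Under Protocol and Treatment Plan, the underlying data are numerical and already averaged: "Three measurements will be taken one minute apart, and the average of each of the systolic and diastolic measurements will be charted" as the recording for the visit.

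On timing, the text after the end points says "Both the primary and secondary outcomes will be measured for every month for the 3 months that the" patient is in the trial. It does not say which month, or whether any or all months, define success.

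Study design gives "20 patients per group". Limitations says: "This is a pilot study and therefore it is may not be powered to detect difference with treatment". The protocol states no blood pressure SD, expected effect, placebo response rate, significance level or test.

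**The concern.** A cut-point applied to a continuous change treats a fall of 9 mm Hg as failure and one of 10 as success, and ignores everything else about size. Joining two cut-points with and/or makes the event easier to reach by ordinary visit-to-visit variation, and the 5 mm Hg diastolic limit is the easier of the two under every SD pair used below. Patients with no true change then count as successes in both arms, and the arms look more alike than they are.

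The stake is precision. Expected results says the pilot is to help establish the basis of a larger randomised trial. Planning on blood pressure needs a mean difference and an SD. A difference in responder rates from 20 per arm provides neither and has a wide interval.

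**Working it through.** The protocol has no blood pressure figure to reproduce. It supplies only the two thresholds and n = 20 per arm. Everything else below is an assumption: two-sided 0.05, no dropout, normal changes, correlation 0.6 between SBP and DBP changes, and SDs and effects as listed.

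**Step 1. Chance response at one visit, no true change.** With change SDs σS and σD, the rate is 1 − Φ₂(10/σS, 5/σD; 0.6), where Φ₂ is the bivariate normal distribution function.

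| Change SD, SBP/DBP | SBP alone | DBP alone | Either |
|---|---|---|---|
| 6/4 | 4.8% | 10.6% | 13% |
| 8/5 | 10.6% | 15.9% | 21% |
| 10/6 | 15.9% | 20.2% | 28% |
| 12/8 | 20.2% | 26.6% | 35% |
| 15/10 | 25.2% | 30.9% | 41% |

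The month is not fixed. If a fall at any of the three monthly visits counted, simulation gives about 41% (8/5) to 60% (12/8), taking visits as independent apart from the shared baseline.

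**Step 2. Power at 20 per arm, per-visit SD 12/8, baseline to follow-up correlation r = 0.6.**

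- Change SD = SD × √(2(1 − r)): 12 × √0.8 = 10.7 and 8 × √0.8 = 7.2. The chance rate is 31.6%.
- Treated-arm response rate: 58.1% for a true effect of 8/4, and 64.8% for 10/5.
- Baseline-adjusted SBP: residual SD = 12 × √(1 − 0.36) = 9.6, and standard error = 9.6 × √(2/20) = 3.04. Noncentrality is 8/3.04 = 2.64 or 10/3.04 = 3.29, on 37 degrees of freedom.

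| Effect | ANCOVA, SBP | ANCOVA, DBP | Responders, Fisher | Responders, uncorrected chi-square |
|---|---|---|---|---|
| 8/4 | 73% | 49% | 27% | 37% |
| 10/5 | 89% | 67% | 42% | 54% |

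Power kept relative to adjusted SBP is 27/73 = 37% and 42/89 = 47% with Fisher, and 37/73 = 51% and 54/89 = 61% with chi-square.

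**Step 3. Effective sample size.** For 80% power at 8/4, the adjusted mean needs 2 × (1.96 + 0.842)² × 9.6²/8² = 22.6, so 23 per arm. The usual two-proportion formula for 31.6% against 58.1% needs 54. The ratio is 54/23 = 2.35, so 1 − 23/54 = 57% of the information is lost. At 10/5 the figures are 15 and 35, ratio 2.33, again a 57% loss.

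**Step 4. Sensitivity.**

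- SD 12/8, r = 0.7 (chance rate 27%), effect 10/5: ANCOVA 95%, Fisher 55%, chi-square 66%.
- SD 15/9, r = 0.6 (change SD 13.4/8.0, chance rate 36%), effects 8/4, 10/5 and 12/6: ANCOVA 54%, 73%, 87%; Fisher 19%, 30%, 44%; chi-square 28%, 41%, 56%.
- Over 60 scenarios (SD 12/8 or 15/10, r 0.4 to 0.8, effects 5/3 to 12/7), the responder analysis needs about 1.7 to 2.7 times as many patients. That is a loss of about 43% to 63% of the effective sample size. Power kept ranges from 46% to 98% with the uncorrected two-proportion test (normal approximation) and from 27% to 93% with Fisher.

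**The case against.** **Assumed inputs.** Apart from n and the thresholds, every input is assumed. This stands, and is why ranges are given. The direction does not depend on it: adjusted mean SBP had the higher power in every scenario.

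**Over half the power lost.** A reader might infer that the endpoint discards more than half the power. The protocol does not support that as a general statement, because it names no test and gives no SD. The inference holds with Fisher's test at small to moderate effects, and part of that loss is Fisher's conservatism at 20 per arm. At SD 12/8 and r = 0.7 the endpoint keeps 55% or 66% against 95%, which is well over half.

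**Bias.** A reader might also infer that chance responses, or regression to the mean in patients enrolled for high pressure, bias the comparison. They do not: randomisation and blinding make them equal in expectation in both arms.

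**Normotensive patients.** Entry is possible through proteinuria or eGFR loss, so a fall in a patient with normal pressure counts as success. That is true, but an ANCOVA includes the same patients. It argues for showing results by baseline hypertension, not for the change of endpoint.

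**Comparator.** SBP is the more favourable choice; adjusted DBP has 49% and 67% in Step 2. It still exceeds both responder tests there, but two co-equal tests would raise multiplicity, so DBP belongs in a supportive role.

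**Pilot, secondary endpoint, analysis plan not shown.** All are fair. The visit values are charted, so means and SDs can be computed later, and an analysis plan may add them. None of this alters the endpoint as the protocol words it.

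**Conclusion.** The point holds in moderate form. The protocol fixes an either/or threshold where it already collects the numbers for a more precise comparison. Under the stated SD assumptions, 13% to 41% of patients with no true change would meet it at one visit. The cost is roughly half the effective sample size, with the loss in power depending on test, SD and effect. The comparison remains valid; it is diluted. The conclusion rests on approximately normal changes, the assumed SDs and correlations, and judging response at a single visit. It is an improvement worth making to a secondary endpoint of a declared pilot, not a flaw that invalidates the trial.

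**What to change.** Reword the blood pressure secondary endpoint as the between-arm difference in clinic SBP at month 3, adjusted for baseline SBP by ANCOVA, with a 95% confidence interval. Analyse DBP in the same way as supportive. Keep the 10/5 responder rate as a descriptive summary, shown separately for SBP and DBP and by hypertension at baseline.

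Naming month 3 also settles the time point for this endpoint. The same threshold appears in Criteria for Response, which governs the week-4 dose step; that is a separate matter and this change leaves it untouched.

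The cost is one change of wording and a standard regression, with no extra patients, visits or measurements. The drawback is that a mean difference is less directly clinical than a responder rate, which the descriptive summary preserves.

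### Placebo tablets are doubled for everyone after week 4 but active tablets only in tolerating non-responders, so tablet count reveals the arm of every week-4 responder in a double-blind trial

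*Protocol*

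**What the plan says.** The Study design section of the protocol plans 20 patients per group and states: "The study will be double-blinded".

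- **Group 1 (active).** Patients start on one 60 mg tablet daily. After 4 weeks, "if tolerated but response is not achieved, the dose will be escalated to Imdur 120 mg ER daily", which means two 60 mg tablets. Protocol and Treatment Plan gives the same escalation for patients without a response.
- **Group 2 (placebo).** "The tablets of placebo will be doubled after 4 weeks of start of therapy". Neither tolerance nor response is mentioned as a condition. The next sentence gives the purpose as reducing bias in a double-blind study.

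Response is defined under "Criteria for Response (one or more of the following"): an eGFR improvement of at least 25%, a proteinuria reduction of at least 25%, or a fall of at least 10 mm Hg systolic and/or 5 mm Hg diastolic. The proteinuria criterion is also the primary end point, and the other two are the secondary end points. All are assessed monthly for 3 months.

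The side-effect rules are worded in mg of active drug. Under Monitoring/Evaluation During Study, a patient with side effects at 120 mg goes back to 60 mg ("If side effects (nausea, dizziness, headache, symptomatic hypotension) are observed to the increased" dose). Criteria for Removal repeats that step-down and takes a patient with side effects at 60 mg off drug; it then adds "Criteria for removal would be uncontrolled nausea, headache", and names two further symptoms. Neither section describes a placebo counterpart.

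**The concern.** Doubling the placebo is meant to protect the blind. It can do so only if the tablet count follows the same rule in both arms. Here one arm has a conditional rule and the other an unconditional one, so among responders the count follows the arm.

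There is also a practical difficulty. A blinded clinician cannot carry out an escalation rule that differs by arm. Either someone who knows the allocation sets the tablet count, or the staff depart from the text.

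Outcome rounds remain after week 4, and two features of the plan are open to influence by anyone who infers the arm. ACE inhibitors or calcium channel blockers are given as needed in both groups, and the Limitations section already doubts whether other antihypertensives will confound the results. Patients also record their own blood pressure at home and report it.

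**Working it through.** **Inputs.** The planned arm size is 20 (Study design). The week-4 dosing rules are those of Groups 1 and 2. The protocol gives no week-4 response rates, so let r_A and r_P be the shares of the active and placebo arms that have met any response criterion by week 4. For simplicity, assume that every active patient tolerates 60 mg and that simple randomization yields exactly 20 and 20.

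**Step 1: tablets per day just after week 4, as written.**

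| Status at week 4 | Active | Placebo |
|---|---|---|
| Responder | 1 | 2 |
| Tolerating non-responder | 2 | 2 |
| Side effects at 60 mg | 0 (off drug) | no rule stated beyond the general doubling |

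**Step 2: what the count reveals.**

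- One tablet: P(active) = 20r_A / (20r_A + 0) = 1, for any r_A above 0. Response status need not be known.
- Two tablets in a known responder: P(active) = 0 / (0 + 20r_P) = 0, for any r_P above 0.
- Two tablets in a tolerating non-responder: P(active) = 20(1 − r_A) / [20(1 − r_A) + 20(1 − r_P)]. This is the probability given non-response alone, so the count adds nothing. With equal response rates it is 50%.

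Clinic staff can know response status, because BP, eGFR and UPC (the urine protein:creatinine ratio) are measured monthly. For staff the responder row is therefore fully informative.

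A patient found on one tablet later could be an active patient stepped down from 120 mg. That patient is still on active drug, and no placebo step-down is described that would make the count ambiguous.

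**Step 3: how many are revealed.** The number is 20r_A + 20r_P, which can lie anywhere from 0 to 40. All rates below are assumptions.

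| r_A | r_P | Active revealed | Placebo revealed | Total of 40 |
|---|---|---|---|---|
| 10% | 10% | 2 | 2 | 4 |
| 30% | 30% | 6 | 6 | 12 |
| 50% | 50% | 10 | 10 | 20 |
| 70% | 40% | 14 | 8 | 22 |

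**Step 4: after the fix.** With one condition for both arms, responders take one tablet and tolerating non-responders take two, whatever the arm. Then P(active given one tablet) = 20r_A / (20r_A + 20r_P), the probability given response alone. At 30% in both arms this is 6/12 = 50%, against 100% as written.

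**The case against.** **The placebo sentence may be shorthand for mirroring the active arm.** Its stated purpose is to reduce bias, and blinded staff could hardly apply two rules. That may be the intention. But Group 1 states its condition and Group 2 states none, and a statement of purpose does not supply a matching condition. If mirroring is meant, the fix simply records it. The certainty in Step 2 does rest on the literal reading.

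**The outcomes are largely objective.** This stands as a limit on the harm. UPC and serum creatinine come from laboratory samples, and clinic BP is the average of three automated readings. A reader might infer that the primary end point is directly biased because it is also a response criterion. The documents do not support that: any effect on UPC would come mainly through co-treatment, and the protocol gives nothing from which to size it.

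**Two further readings are tempting and do not hold.**

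- *That the stopping rules contradict each other.* Criteria for Removal says that if the starting dose caused "these effects, then the patient will be taken off the drug, and will be observed for Intension to Treat" analysis, and then adds "Criteria for removal would be uncontrolled nausea, headache", symptomatic hypotension or dizziness. The section before it says of headache and dizziness that the "symptoms are dose dependent and tend to disappear with continued use", so mild early symptoms might seem to fall between the two sentences. But both stand under one heading, and the second reads naturally as the threshold for the first. The practical gap may be zero.
- *That every two-tablet patient becomes less likely to be on active drug.* At 30% response in both arms, pooling gives 14/34 = 41%. That mixes non-responders (14 active against 14 placebo, 50%) with 6 placebo responders (0%), and describes neither group.

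**Conclusion.** The escalation rules are wrong as written for a double-blind trial, and nothing elsewhere in the protocol repairs them. Followed literally, they reveal the arm of every patient who has met a response criterion by week 4, in both groups, while leaving tolerating non-responders masked. A reader might infer that the whole trial is unblinded; the rules do not go that far.

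The logic needs no assumed rate, but the number affected does: 4, 12 or 20 of 40 at assumed response rates of 10%, 30% or 50% in both arms. The main exposure is as-needed antihypertensive treatment and home-recorded BP. The size of any resulting bias cannot be derived from the document. Because the defect is clear on the text and the repair is cheap, it should be corrected.

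**What to change.** In Study design, and in the matching sentence of Protocol and Treatment Plan, replace the separate Group 1 and Group 2 escalation rules with one rule worded by tablet count. For example: at week 4, in either group, a patient who tolerates one tablet and has not met the response criteria goes to two tablets; all others who tolerate one tablet stay on one.

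Reword the side-effect rules in Monitoring/Evaluation During Study and Criteria for Removal the same way: from two tablets back to one, or from one tablet to none, applied blinded in both groups. Keep the existing provision that a patient taken off drug is still observed for the intention-to-treat analysis.

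The cost is a wording amendment and a matching dispensing instruction to the pharmacy. No patients, visits or tests are added, because BP, eGFR and UPC are already measured monthly in both groups.
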